5.4.3. Exploratory endpoints

Study Part 1 and 2:

- Assessment of PD activity of SEL24/MEN1703 by changes between pre- and post-treatment levels of p-Ser235/6 S6 and other relevant biomarkers as appropriate, in peripheral blood by using flow cytometry;
- Analysis of relevant mutations in peripheral blasts and bone marrow by using Next Generation Sequencing and/or qRT-PCR. The mutational status of patients before and after treatment with SEL24/MEN1703 will be assessed by the analysis of a panel of relevant AML mutated genes in bone marrow.

5.4.4. Safety endpoints

Safety endpoints are included among primary and secondary endpoints (Sections 5.4.1 and 5.4.2).

5.4.5. PK endpoints

Study Part 1 and 2:

The PK profile of SEL24/MEN1703 and its metabolites, as appropriate, will be evaluated by analysis of concentration levels in plasma. Nominal PK blood sampling times should be adhered to as closely as possible. It is essential that the actual time and date of collection of each blood sample are recorded in the patient's records and in the eCRF. Left over sample aliquots could be analysed for metabolite identification purposes. The results of the metabolite identification analysis will be reported separately.

The following PK parameters will be derived, where appropriate, from the individual plasma concentration versus time profiles of SEL24/MEN1703 and its metabolites:

- C_{\max} : the maximum observed concentration.
- t_{\max} : the time at which C_{\max} was apparent,
- C_t or C_{last} : the last quantifiable concentration,
- t_{last} : the time of the last quantifiable concentration,
- AUC_{0-t} or AUC_{last} : the area under the concentration versus time curve from time zero to t_{last} , calculated by the linear trapezoidal rule,
- AUC_{0-24} : the area under the concentration versus time curve from time zero to 24 hr, calculated by the linear trapezoidal rule.
- AUC_{extrap} : the extrapolated area under the concentration-time curve, calculated as C_t/λ_z ,

- $AUC_{0-\infty}$: the area under the concentration-time curve estimated from time zero to infinity as the sum of AUC_{0-t} and AUC_{extrap} ,
- λ_z : the apparent terminal rate constant, estimated using the negative slope of the least square regression analysis of the log concentration versus time data for the terminal linear portion of the curve,
- $t_{1/2}$: the apparent terminal half-life, calculated from $\ln(2)/\lambda_z$.
- CL/F : the apparent clearance calculated as Dose/ $AUC_{0-\infty}$,
- CL_{ss}/F : the apparent clearance at steady state, calculated as Dose/ AUC_{0-t} ,
- V_z/F : the apparent volume of distribution based on the terminal phase, calculated as CL/λ_z .

Additional PK parameters may be calculated as appropriate.

Study Part 1

Urine samples will be collected from the first dose of SEL24/MEN1703 until 24 hours. The following PK parameters will be derived, where appropriate, from the individual urine samples of SEL24/MEN1703 and its metabolites:

- $Ae_{(0-x)}$: the urinary recovery of analyte over the collection interval, calculated as the sum of the amounts excreted over each collection interval. The amount excreted in urine for each collection interval is calculated as the product of the urine concentration and the urine volume.
- f_e : the fraction excreted, namely the fraction of the dose recovered unchanged in urine over the collection interval,
- CLR : the renal clearance, calculated from the fraction extracted multiplied by the total plasma clearance.

6. General specifications

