- ~ PK sampling (blood; 22-26 h post C1 D14 dose)

Note: PK sampling times are relative to last dose in C1.

Cycle 1, Day 17

- ~ PK sampling (blood; 70-74 h post C1 D14 dose)

Note: PK sampling time is relative to last dose in C1.

Cycle 1, Day 19

- ~ PK sampling (blood; 118-122 h post C1 D14 dose)

Note: PK sampling time is relative to last dose in C1.

Cycle 2, Day 1

- ~ ECOG PS
- ~ Vital signs
- ~ FSH/Pregnancy testing
- ~ Physical examination
- ~ Clinical chemistry
- ~ Hematology
- ~ Coagulation
- ~ Lipid profile
- ~ Urinalysis
- ~ ECG
- ~ PD biomarkers (blood; pre-dose)
- ~ Adverse events
- ~ Transfusion status
- ~ Concomitant medication
- ~ PK sampling (blood; pre-dose)

Cycle 2, Day 7

- ~ Clinical chemistry
- ~ Hematology
- ~ Coagulation
- ~ Adverse events
- ~ Transfusion status
- ~ Concomitant medication
- ~ PK sampling (blood; 2-6 h post dose)

Cycle 2, Day 14

- ~ Clinical chemistry
- ~ Hematology
- ~ Coagulation
- ~ Lipid profile
- ~ Peripheral blasts

- ~ PD biomarkers (blood; 2-6 h post dose)
- ~ Adverse events
- ~ Transfusion status
- ~ Concomitant medication
- ~ PK sampling (blood; 2-6 h post dose)

#### Cycle 3 onwards, Day 1

- ~ ECOG PS
- ~ Vital signs
- ~ FSH/Pregnancy testing
- ~ Physical examination
- ~ Clinical chemistry
- ~ Hematology
- ~ Coagulation
- ~ Lipid profile
- ~ Urinalysis
- ~ ECG
- ~ Bone marrow aspirate/biopsy (mandatory as soon as peripheral lab results become consistent with an objective response and at Cycle 3; recommended every 2 cycles thereafter)
- ~ Disease evaluation (optional; recommended every 2 cycles)
- ~ Genetic profiling (bone marrow, recommended every 2 cycles)  
Note: An aliquot of bone marrow aspirates/biopsy will be used
- ~ PD biomarkers (blood; pre-dose)
- ~ Adverse events
- ~ Transfusion status
- ~ Concomitant medication
- ~ PK sampling (blood; pre-dose)

#### Cycle 3 onwards, Day 14

- ~ Clinical chemistry
- ~ Hematology
- ~ Peripheral blasts
- ~ PD biomarkers (blood; 2-6 h post dose)
- ~ Adverse events
- ~ Transfusion status
- ~ Concomitant medication
- ~ PK sampling (blood; 2-6 h post dose)

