15. Blood samples for plasma PK analysis will be taken at C1 D1 pre-dose, 0.5, 1, 2, 4, 6, 8, 10-14 and 24 h (C1 D2 pre-dose), C1 D7 at 4 and 8 h post dose, C1 D14 (or last day of dosing in cycle) pre-dose, 0.5, 1, 2, 4, 6, 8, 10-14 and 24 h (C1 D15), 72 h (C1 D17), 120 h (C1 D19), C2 D1 pre-dose (-1 d tolerance), D7 and 14 (or last day of dosing in cycle) at 2-6 h post dose, C3 onwards D1 pre-dose (-1 d tolerance) and D14 (or last day of dosing in each cycle) at 2-6 h post dose (-2 d tolerance). All sample times are approximate, and every effort should be made to take the samples as close to the specified time given and, where relevant, contemporaneously with blood sampling for PD biomarker assessments. For the C1 D1, D2, D7 and D14 a ±5 min window is allowed, for the C1 last day of dosing 24 h (C1D15), 72 h (C1D17) and 120 h (C1D19) samples, a ±2 h window is allowed. Please refer to the Lab Manual for full details on sample collection, time-points, processing, storage and shipment.
16. Part 1 only. Urine collection for PK analysis will be collected from the first dose of SEL24/MEN1703 until immediately prior to the second dose. Please refer to the Lab Manual for full details on sample collection, time-points, processing, storage and shipment.
17. Final study assessments to be conducted up to 30 d (+/- 2 d) from last dose of SEL24/MEN1703. Adverse events and concomitant medications must be assessed to 30 d from last dose of SEL24/MEN1703. Other assessments may be carried out between 7-30 d from last dose.
18. An assessment of each patient's disease status will be made approximately every 3 months from last dose of SEL24/MEN1703 for up to 1 year regardless of initiation of additional treatments to determine date of progression (where appropriate) and survival status.

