12.3. Pharmacokinetic analysis

The PK analysis will be run on the PK population.

Plasma concentration values Below the Lower Limit Of Quantification (BLLOQ) will be set to zero before the t_{max} and to “missing” after the t_{max} . Plasma concentrations reported as $>$ BLLOQ at time zero, when the subject has not previously been dosed, will be set to their real value. Data-replacements will be implemented by the Global Clinical Pharmacology and Pharmacometrics department. A footnote should be added to the listing, tables, and figures, in order to indicate the LOQ value.

If actual sampling time is missing, the nominal time will be used.

If the 24-hours post dose sample is collected after the intake of the following dose, the corresponding concentration will be reported in the listing with a FLAG and excluded from the PK parameter calculation.

If urine volume is missing, concentrations will be reported in the listing and no PK parameters will be calculated.

If samples are collected during an unscheduled visit, individual concentrations and PK parameter will be reported in the listing with a FLAG, but they will be excluded from the summary statistics.

All PK plasma and urine concentrations and PK parameters will be summarized by cohort, cycle, day, IDH mutational status, and nominal time point, and by dose, cycle, day, IDH mutational status and nominal time point, by using the following descriptive statistics:

- Number of non-missing observations (N),
- Arithmetic mean (AM) and its 90% confidence interval (CI), standard deviation (SD), coefficient of variation (CV%) and standard error (SE),
- Geometric mean (GM) and its 90% CI and GM CV%,
- Median,
- Minimum (min) and maximum (max).

Individual plasma concentration data versus time will be presented in a data listing and visualized as individual concentration-time plots. Individual urine concentration data will be presented in a data listing.

Actual times will be used for calculation of PK parameters and replaced by nominal times when missing. Plot of individual and aggregated concentration versus time curves will be generated with nominal times.

13. Tables, listings and figures

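### Day 14 AUC0-t is integrated by the linear trapezoidal rule across two 48-hour sampling gaps, which overstates it, and AUC0-inf, by an amount that depends on half-life

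*SAP*

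**What the plan says.** SAP 5.4.5 defines AUC0-t (also called AUC_last) from time zero to t_last, "calculated by the linear trapezoidal rule". Protocol Table 14 gives the same rule, and neither document provides a logarithmic rule for the declining part of the curve. In SAP 5.4.5, AUC0-inf is AUC0-t plus C_t/λz. CL/F is Dose/AUC0-inf, CLss/F is written as Dose/AUC0-t, and Vz/F is CL/λz.

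Footnote 15 to the SAP 5.3 flow chart ends the Cycle 1 Day 14 profile at "24 h (C1 D15), 72 h (C1 D17), 120 h (C1 D19"; protocol Table 5 has the same schedule. The late samples have a window of ±2 h; protocol 5.1, for example, places the Day 17 sample at "70-74 h post C1 D14 dose".

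SAP 12.3 states that "Actual times will be used for calculation of PK parameters", with nominal times where these are missing. Values below the quantification limit become missing after t_max. PK parameters are summarised by cohort and by dose, cycle and day, for the parent drug and for MET3 (SAP 13.2.1, Tables 4.2 and 4.6).

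**The concern.** The schedule leaves two 48 h gaps at the end of the Day 14 profile. The SAP treats the terminal phase as exponential: λz comes from a regression on log concentration, and the extrapolated area is C_t/λz. Up to t_last, however, it joins the same phase with straight lines. The two halves of AUC0-inf thus rest on different shapes, and the straight-line half can only err upward where the decline is exponential.

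AUC is a named PK variable under a secondary objective in both parts of the study. The error is not a constant that could be ignored when patients are compared. It changes with half-life, and it appears only when t_last is 72 h or 120 h. Protocol 5.3.15 notes that the drug may be both a substrate and an inhibitor of CYP2D6 and has patients phenotyped for it, so half-lives may well differ between patients.

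**Working it through.** The plan states no figure for AUC error, so there is none to reproduce.

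**Inputs from the documents:** the linear rule (SAP 5.4.5, protocol Table 14); once-daily dosing for 14 days; Day 14 samples at 0, 0.5, 1, 2, 4, 6, 8, 10-14, 24, 72 and 120 h (SAP 5.3).

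**Assumptions:** half-life is defined but given no value, so 6 to 72 h is taken. The absorption rate ka is taken as 0.3 to 2.0 per h, and the 10-14 h sample as 12 h. The model is one-compartment and oral: with k = ln 2 / t½, concentration at time t after dose 14 is proportional to the sum over i = 0 to 13 of [exp(−k(t+24i)) − exp(−ka(t+24i))].

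**Step 1: one gap.** For exponential decline over D = 48 h, put x = D·ln 2 / t½. Then linear area / true area = (x/2)(1 + e^−x)/(1 − e^−x), which exceeds 1 for every finite half-life. At t½ = 24 h, x = 1.386 and e^−x = 0.25, so the ratio is 0.693 × 1.25/0.75 = 1.155. The area in the gap is overstated by g = 15.5%. At 12 h, x = 2.773 and e^−x = 0.0625, so the ratio is 1.386 × 1.0625/0.9375 = 1.571 and g = 57.1%.

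**Step 2: whole profile.** Let R be true AUC0-120 / true AUC0-24, and e24 the linear-rule error in AUC0-24. Both gaps are 48 h wide, so the total error is E = g(1 − 1/R) + e24/R. At t½ = 24 h and ka = 1.0, R = 1.965. Then E = 15.5 × 0.491 + 0.2/1.965 = 7.6 + 0.1 = 7.7%, which agrees with direct numerical integration.

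| t½ | g | R (ka 1.0) | e24 (ka 1.0) | E (ka 1.0) | E over ka 0.3-2.0 |
|---|---|---|---|---|---|
| 6 h | 179.4% | 1.075 | +3.1% | +15.4% | +14.7 to +19.9% |
| 8 h | 114.5% | 1.156 | +2.1% | +17.3% | +16.7 to +20.4% |
| 12 h | 57.1% | 1.352 | +1.1% | +15.7% | +15.4 to +17.0% |
| 16 h | 33.7% | 1.563 | +0.6% | +12.5% | +12.4 to +13.1% |
| 24 h | 15.5% | 1.965 | +0.2% | +7.7% | +7.7 to +7.9% |
| 36 h | 7.0% | 2.463 | +0.1% | +4.2% | +4.2% |
| 48 h | 4.0% | 2.837 | 0.0% | +2.6% | +2.6% |
| 72 h | 1.8% | 3.344 | 0.0% | +1.2% | +1.2% |

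The error is not monotone: as a share of AUC0-t it peaks near 8 h.

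**Step 3: dependence on t_last.** If the 120 h sample is below the limit but the 72 h sample is not, the error is still +16.5 to +20.2% at 8 h and about +7% at 24 h. If both are below the limit, t_last is 24 h and the gaps drop out, leaving about +2% at 8 h. The modelled 72 h level is under 0.1% of Cmax at 6 h, about 0.3 to 0.4% at 8 h (ka 0.4 to 1.0), about 2 to 3% at 12 h and 13 to 16% at 24 h.

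**Step 4: derived quantities.** At 24 h, AUC0-inf is high by 7.5 to 7.6%. CL/F and Vz/F are then low by about 7.5/107.5 = 7.0%.

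**Step 5: the alternative rule.** Linear-up/log-down replaces each falling trapezoid by Δt(C1 − C2)/ln(C1/C2). On the same samples and model the AUC0-120 error is −1.3% to 0.0% over the whole assumed range. That model favours the rule, because log-down is exact for mono-exponential decline. With assumed bi-exponential profiles (half-lives 6-8 h and 36-60 h, fast fraction 0.8-0.95), log-down erred by +1.4 to +4.2% and linear by +4.2 to +10.6%.

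**The case against.** Several counter-arguments have force.

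- **The size is assumed.** With no half-life or quantification limit in the documents, the error could be 1% or 20%. The largest values occur at half-lives for which the 72 h level is a fraction of a percent to a few percent of Cmax and may not be quantifiable. This stands, and it is why only a conditional range is given.
- **Dose comparison has a safer measure.** SAP Figures 23 and 26 plot Cmax and AUC24 against dose, and AUC24 ends before the gaps. This stands. A reader might infer that the trial's exposure-versus-dose picture is distorted; those figures do not support that.
- **The remedy does not cure unequal t_last.** Late samples may be quantifiable more often at higher doses, and one could attribute the resulting differences in AUC0-t to the trapezoidal rule. Most of that effect is truncation. True AUC0-120 is about 1.35 to 1.39 times AUC0-24 at 12 h (ka 0.4 to 1.0) and about 2 times at 24 h, against trapezoid errors of about 16% and 8%. No integration rule removes it.
- **Little depends on it.** PK is secondary and descriptive, and no test or sample size uses AUC. Protocol 1.4 gives the DLTs at 150 mg as the reason for settling on 125 mg, so the documents do not support reading this as a threat to the recommended dose.
- **An SOP might govern.** SAP 6.5 lists a procedure on standard non-compartmental methods, by title only. Its content is not available and cannot be assumed to override explicit text in both documents.

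**Conclusion.** The concern holds for Day 14 AUC0-t and for what is built on it: AUC0-inf, CL/F and Vz/F, and CLss/F as written. If the AUC in CLss/F was meant to cover one dosing interval, that parameter escapes the gaps. Under exponential decline the direction of the error is certain: AUCs too high, clearances and volume too low.

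Its size rests on an undocumented half-life and quantification limit and on a one-compartment model. It is material at half-lives up to about 24 h if the 72 h sample is quantifiable, and small from 36 h upward. MET3 is integrated by the same rule on the same schedule, so the direction applies to its declining phase too, but its kinetics were not modelled and no size is claimed.

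Day 1 AUC0-t and AUC0-24 contain no 48 h gap. A reader should not conclude that all reported exposure is biased, or that log-down would be exact. This is a limited but avoidable bias, worth correcting because the correction is cheap and needs no new samples.

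**What to change.** In SAP 5.4.5, state that AUC0-t, AUC0-24 and the observed part of AUC0-inf are all calculated by the linear-up/log-down rule, for parent drug and MET3. In SAP 3.1, declare this as a change from protocol Table 14, since that section now says all analyses are as the protocol specifies. Add a sentence to SAP 12.3 that comparisons between doses rest on AUC0-24, because AUC0-t also varies with t_last whichever rule is used.

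The cost is one setting in the non-compartmental software and a few sentences. Reported Day 14 AUC0-t and AUC0-inf will be somewhat lower. They will also be less directly comparable with any earlier results computed by the linear rule. Protocol 1.4 compares human and dog AUC0-t without saying which rule was used. If that comparison must be kept, a linear-rule AUC0-t can be listed alongside as a sensitivity value.

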6.1. Data validation

Medidata Classic Rave® 2021.1.4 is used as Electronic Data Capture system for data entry, by site personnel and for data cleaning and data locking by the Menarini Data Management team.

The eCRF data have been elaborated to create the SDTM (v1.7) and ADaM (v2.1) datasets based on CDISC standards.

6.2. Computer system and software used

The software used for all summary statistics and statistical analyses will be SAS® 9.04.01, SAS® Studio version 3.8 or higher (SAS Institute, Inc.). All tables and listings will be produced using PROC REPORT or procedure specific output displays using output delivery system (ODS). The summary tables and listings will use SAS monospace font of size 6. The default page type will be A4 and the default page orientation will be landscape.

Pharmacokinetic parameters (described in section 2.4.5 – PK endpoints) will be derived from individual measured concentrations using non-compartmental analysis (NCA) with a fully validated Phoenix™ WinNonlin (WNL) software, version 7 or higher (Pharsight®, Mountain View, California).

6.3. Coding systems

6.3.1. Clinical Terms

Concomitant diseases, medical procedures, and Adverse Events are coded with MedDRA version 23.1 or following versions.

6.3.2. Drugs

Drugs will be coded with WHO (ATC coding system) Drug version Sep-2020.

6.3.3. Classification criteria

Adverse Events are graded for severity using the classifications of Common Terminology Criteria for Adverse Events (CTCAE) Version 4.03 (June 14, 2010). Further details about NCI CTCAE classification are specified in protocol version 12.0, section 7 and appendix C.

6.4. Report type, language, format

The statistical output will be in .pdf format and in English language.

- Dates will be presented with the DDMMYY format.
- Counts and percentages:
$$<\text{group 1}> \quad \text{xxx}/(\text{xxx.x}\%)$$
- Counts and percentages including also the count of the event of interest:
$$<\text{group 1}> \quad \text{xxx}/(\text{xxx.x}\%)|\text{xxx}$$
- Descriptive statistics, laboratory parameters summary statistics:

N	xxx
Mean	xxx.xx
Median	xxx.xx
SD	xxx.xxx
Minimum	xxx.x
Maximum	xxx.x

Character values will be left aligned.

6.5. Standard Operating Procedures (SOPs) to be followed

¹ Code	Title
MR-GCS-DMST-210_SOP	Statistical Analysis Plan (SAP)
MR-GCS-DMST-211_SOP	Statistical Programs Writing
MR-GCS-DMST-211.3_WI	TLF programming
MR-GCS-CP&P-504	Use and management of Phoenix® WinNonlin® and pharmacokinetic data flow
MR-GCS-CP&P-505	Standard methods for non-compartmental analysis of pharmacokinetic data

6.6. Data Transfer Agreements

CD25 data

Data Transfer Agreement (DTA) between [REDACTED] and Menarini Ricerche S.p.A., version 2.0 of 29th January 2021.

CYP2D6 data

Data Transfer Agreement (DTA) between [REDACTED] and Menarini Ricerche S.p.A., version 3.0 of April 2021.

Data Management Plan

Data Management Plan V2.0 (2021).

Genetic Profile data

Data Transfer Agreement (DTA) between [REDACTED] and Menarini Ricerche S.p.A., version 2.0 of 28th April 2021.

Pharmacodynamics data

Data Transfer Agreement (DTA) between [REDACTED] and Menarini Ricerche S.p.A., version 2.0 of 29th January 2021.

Pharmacokinetics data

Data Transfer Agreement (DTA) between [REDACTED] and Menarini Ricerche S.p.A., version 1.0 of 14th April 2020.

Data Transfer Agreement (DTA) between [REDACTED] and Data Management & Clinical Sciences Unit of Menarini Ricerche S.p.A. – Statistics and Data Management Unit, version 4 of April 2023.

7. Definitions and general methodology

7.1. Data quality assurance

All tables, figures and data listings to be included in the report will be independently checked for consistency, integrity and in accordance with Menarini Ricerche standard procedures.

7.2. General considerations and key definitions

7.2.1. General considerations

Study day is defined as the number of days from the date of first dose of MEN1703 to the event/visit date.

7.2.2. Key definitions

Baseline values

The baseline value of an assessment is defined as the last available (non-missing) value before or on the date of first administration (Day 1) for Cycle 1.

Adverse Events (AEs)

An AE is any untoward medical occurrence in a patient (or a clinical investigation subject), receiving a medicinal product and which does not necessarily have a causal relationship with the treatment. Therefore an AE can be any unfavourable and unintended sign (including an abnormal clinically significant laboratory finding), symptom, or disease temporally associated with the use of a medicinal (investigational) product, whether or not related to the medicinal (investigational) product. All identified AEs are recorded and described on the appropriate AE page of the eCRF, except for those events occurring prior to the first dose of study medication, which are recorded on the Medical History eCRF page.

Adverse Drug Reactions (ADRs)

Untoward and unintended responses to an Investigational Medicinal Product (IMP) related to any dose administered. The definition covers also medication errors and uses outside what is foreseen in the protocol, including misuse and abuse of the product. The definition implies a 'reasonable possibility of a causal relationship between the event and the IMP. This means that there are facts (evidence) or arguments to suggest a causal relationship.

All AEs (including SAEs) have to be accurately recorded on the AE page of the patient's eCRF. Each event will be graded for severity using the classifications of NCI CTCAE v4.03. For events not addressed in the NCI CTCAE v4.03, classifications will be performed according to the following grading:

- Mild (Grade 1) - Mild; asymptomatic or mild symptoms; clinical or diagnostic observations only; intervention not indicated;
- Moderate (Grade 2) - Moderate; minimal, local or noninvasive intervention indicated; limiting age-appropriate instrumental activity of daily living;
- Severe (Grade 3) - Severe or medically significant but not immediately life-threatening; hospitalization or prolongation of hospitalization indicated; disabling; limiting self-care activity of daily living;
- Life-threatening (Grade 4) - Life-threatening consequences; urgent intervention indicated.

- Death (Grade 5) - Related to adverse event.

Serious Adverse Event (SAE) / Serious Adverse Drug Reaction (SADR)

An SAE is defined as any untoward medical occurrence that at any dose causes or qualifies as the following:

- Results in death.
- Is life-threatening:
 - “Life-threatening” means that the patient was at immediate risk of death at the time of the SAE; it does not refer to an SAE that hypothetically might have caused death if it were more severe.
- Requires hospitalization or prolongation of existing hospitalization:
 - This means that hospital inpatient admission or prolongations of hospital stay were required for the treatment of the SAE or that they occurred as a consequence of the event.
 - Visits to a hospital by ambulance or to the emergency room without admission will not be regarded as hospitalization unless the event fulfills any other of the serious criteria.
- Results in persistent or significant disability or incapacity:
 - “Persistent or significant disability or incapacity” means a permanent or significant and substantial disruption of a person’s ability to carry out normal life functions.
- Is a congenital anomaly or birth defect.
- Is an important medical event:
 - Medical and scientific judgment should be exercised in deciding whether expedited reporting is appropriate in situations where none of the outcomes listed above occurred. Important medical events that may not be immediately life-threatening or result in death or hospitalization but may jeopardize the patient or may require intervention to prevent one of the other outcomes listed in the definition above should also usually be considered serious. Examples of such events include allergic bronchospasm requiring intensive treatment in an emergency room or at home, blood dyscrasias, or convulsions that do not result in inpatient hospitalization, or the development of drug dependency or drug abuse.

All patients with SAEs must be followed up for outcome until it is considered resolved, returns to baseline, is chronically ongoing, stabilized, or is otherwise explained by the Investigator.

Exceptions to SAE

For this study, the following events will be considered to be expected events in this population and during leukemia therapy (e.g. myelosuppression and events secondary to disease) and should not be reported to the Sponsor as serious events unless the Investigator considers any of these events to be clinically concerning and of unusual manifestation with regard to severity, duration, frequency, outcome or other characteristics of the event. It is important to note that these events (with the exception of progression of AML, consider unrelated to study drug), still need to be captured as AEs on the AE eCRF and will be reviewed by the DMC in aggregate with all cumulative safety data.

Expected events during leukemia therapy are:

- Myelosuppression due to disease or leukemia therapy:
 - Febrile or infection episodes.
 - Epistaxis or bleeding except for catastrophic CNS or pulmonary hemorrhage.
 - Anemia, neutropenia, lymphopenia, thrombocytopenia, leukopenia, leukocytosis.
- Events due to underlying disease:
 - symptoms associated with anemia:
 - Fatigue.
 - Weakness.
 - Shortness of breath.
 - Electrolyte abnormalities (sodium, potassium, bicarbonate, CO₂, magnesium).
 - Chemistry abnormalities (LDH, phosphorus, calcium, BUN, protein, albumin, uric acid, alkaline phosphatase, glucose).
 - Coagulation abnormalities.
 - Disease specific therapy (induction, maintenance, salvage, or stem cell therapy).
 - Alopecia.
 - Bone, joint, or muscle pain.
 - Liver function test abnormalities associated with infection or disease progression.
 - Disease progression.
- General therapy events:
 - Events attributed to the use, placement and/or insertion of catheters.
 - Renal failure associated with tumor lysis syndrome or antibiotic/antifungal therapy.
 - Rash due to antibiotic use.
- Hospitalization for the management of any of the above expected events.

Abnormal hematologic or clinical chemistry values, not considered to be clinically significant, will not be recorded on the adverse event eCRF, although all values will be recorded on the hematology and clinical chemistry laboratory eCRFs.

Causality Assessment of Adverse Events

All AEs (including SAEs) will be assessed for the relationship of the AE to the study drug using the following standard definitions:

1. **Definitely related:** The event or laboratory test abnormality (AE) has a plausible time relationship to the drug intake and it cannot be explained by a concurrent disease or other drugs. The response to withdrawal of the drug (dechallenge) should be plausible (pharmacologically, pathologically). The event must be definitive pharmacologically or phenomenologically (i.e. an objective and specific medical disorder or a recognised pharmacological phenomenon), using a satisfactory rechallenge procedure if necessary.
2. **Probably related:** The event or laboratory test abnormality (AE) has a reasonable time relationship to the drug intake, it is unlikely to be attributed to a concurrent disease or other drugs and it follows a clinically reasonable response on withdrawal (dechallenge). Rechallenge (AE reappearance after drug reintroduction) is not required to fulfil this definition.
3. **Possibly related:** The event or laboratory test abnormality (AE) has a reasonable time relationship to the drug intake, but it could also be explained by disease or other drugs. Information on drug withdrawal (dechallenge) may be lacking or unclear.
4. **Unlikely related:** The event or laboratory test abnormality (AE), with a time to drug intake that makes a relationship improbable (but not impossible). Disease or other drugs provide plausible explanations.
5. **Not related:** The event or laboratory test abnormality (AE), with a time to drug intake with an unreasonable relationship and or non-plausibility and/or the existence of a clear alternative explanation.

Please also refer to supporting information provided in Appendix C of the study protocol. The relationship of the study treatment to an AE will be determined by the Investigator and subsequently reviewed by the Medical Monitor.

For reporting and data analysis purposes, AEs reported with a causality assessment of “Definitely”, “Probably”, and “Possibly” are to be considered as “having a reasonable causal relationship” to

study drug. In case of disagreement between the Investigator and the Sponsor's Medical Monitor, the more conservative assessment will determine the reportability of the case.

